### Appendix 3. Statistical Methodology Details

#### Appendix 3.1.1. MMRM for Safety Analysis and PD analysis:

##### On raw scale:

```
proc mixed data = dataset method = reml;  
  class subjid treatment day;  
  model cfb = treatment base day base*day day*treatment/ ddfm = kr  
  residual;  
  repeated day / subject = subjid type = un;  
  lsmeans treatment*day / diff cl alpha = 0.1;  
run;
```

##### On natural logarithmic scale:

```
proc mixed data = dataset method = reml;  
  class subjid treatment day;  
  model log(RCBL) = treatment log(base) day log(base)*day day*treatment/ ddfm = kr  
  residual;  
  repeated day / subject = subjid type = un;  
  lsmeans treatment*day / diff cl alpha = 0.1;  
run;
```

#### Appendix 3.1.2. ANCOVA for Safety Analysis and PD Analysis:

##### On raw scale:

```
proc mixed data = dataset method = reml;  
  class treatment;  
  model CFB = treatment base /residual;  
  lsmeans treatment / diff cl alpha = 0.1;  
run;
```

##### On natural logarithmic scale:

```
proc mixed data = dataset method = ml;  
  class treatment;  
  model log(RCBL) = treatment log(base) /residual;  
  lsmeans treatment / diff cl alpha = 0.1;  
run;
```

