#### **Analysis of percent change from baseline:**

The ANCOVA model will include the natural logarithmic transformed of relative change from baseline of the relevant endpoint as specified in [Section 6](#) as the dependent variable and will include treatment as a fixed effect and baseline as a covariate.

Missing values will not be imputed.

The adjusted geometric Least Squares Means (LSMeans) together with 80% confidence intervals and standard errors will be obtained for each treatment. Differences in adjusted geometric LSMeans between each treatment and placebo, together with 80% confidence intervals and standard errors, will also be obtained. All LSMeans and LSMeans differences (including CI's) will be back transformed to provide adjusted geometric LSMeans and ratios of adjusted geometric LSMeans. Then, percent change from baseline will be calculated as follows:

$$\text{Percent change} = 100 * (\text{RCBL} - 1)$$

where RCBL is either the adjusted geometric LSMeans estimate or the ratio of adjusted geometric means coming from the statistical model. The corresponding 80% CIs will be calculated as well.

Standard SAS output will be provided to support the main statistical summary table for the models.

Example SAS code is provided in Appendix 3.

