## 6. ANALYSES AND SUMMARIES

### 6.1. Primary Endpoint

#### 6.1.1. Liver Fat Content Assessed Using MRI-PDFF at Week 6

- Estimand strategy: Estimand 1

Raw data, changes from baseline, and percent changes from baseline will be summarized by treatment, and week as described in [Section 5.2.2](#).

- Figures for summary Outputs:
  - ✓ Box and whisker plots for individual percent change from baseline at Week 6 versus treatment will be presented and overlaid with arithmetic means. Only box, whiskers, median, arithmetic mean, and outliers should be reported in this graphic.

The statistical analysis will be performed using the natural-logarithmic transformation of relative change from baseline as described in [Section 5.2.4](#).

- Statistical outputs:
  - ✓ Adjusted geometric LSMeans estimates with 80% confidence interval for each treatment along with the translation in percent change (with their associated confidence interval),
  - ✓ Ratio of adjusted geometric LSMeans estimates for each active treatment against placebo and the corresponding 80% confidence interval along with the translation in percent difference (with their associated confidence interval). P-values for the ratio of adjusted geometric LSMeans estimates for each active treatment against placebo will be reported as well,
  - ✓ Summary tables reporting MMRM outputs will include the number of participants included in the analysis.
- Figures from statistical outputs
  - ✓ Plot of percent change from baseline after back transformation of adjusted geometric LSMeans with 80% confidence interval over time,
  - ✓ Plot of percent change from baseline placebo-adjusted after back transformation of adjusted geometric LSMeans ratios with 80% confidence interval over time.

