**Appendix 5.2. Box and Whisker Plot for Changes/ Percent Changes From Baseline by Treatment and Week**

**Note:** To be adapted for C3711005 design (eg weeks as legend) with correct total daily dose. Only box, whiskers, median, arithmetic mean and outliers should be reported in this graphic (individual participant data [open circles within 5th and 95th whisker should not be included] only the individual values which are outliers/outside whiskers).

**Appendix 5.3. LS Means and Placebo Adjusted LS Means with 80% CI from MMRM Analysis Over Time Versus Week per Treatment (to be adapted for C3711005 Design)**

**Appendix 5.4. Example for LS Means and Placebo Adjusted LS Means with 80% CI from ANCOVA Analysis at Week 6 per Treatment (to be adapted for C3711005 Design)**

**Appendix 5.5. Example for Figure Reporting Multiple Laboratory Parameters Over Time Simultaneously (to be adapted for C3711005 Design)**

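### SAP text asks for 80% confidence intervals, but all four model code blocks set alpha = 0.1 (90% limits), and the primary block also uses ML where the others use REML

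*SAP*

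**What the plan says.** SAP Section 5.2.4, on percent change from baseline (the method for the primary endpoint), states: "The adjusted geometric Least Squares Means (LSMeans) together with 80% confidence intervals and standard errors will be obtained for each treatment". It sets the same level for the differences from placebo. Section 5.2.5 does likewise for the MMRM estimates. Section 6.1.1 lists among the primary outputs: "Ratio of adjusted geometric LSMeans estimates for each active treatment against placebo and the corresponding 80% confidence interval". The 80% level recurs in 6.2.1 (triglycerides), 6.3.1, 6.3.3 to 6.3.7, 6.6.4.1 (platelets) and 6.6.4.2 (eGFR). It also appears in the titles of Appendix 5.3 and Appendix 5.4, the latter reading "LS Means and Placebo Adjusted LS Means with 80% CI from ANCOVA Analysis at Week 6 per Treatment".

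Sections 5.2.4 and 5.2.5 both send the reader to the code: "Example SAS code is provided in Appendix 3". Appendix 3 holds four PROC MIXED blocks:

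- The two MMRM blocks (Appendix 3.1.1, raw and log scale) end with "lsmeans treatment*day / diff cl alpha = 0.1".
- The two ANCOVA blocks (Appendix 3.1.2, raw and log scale) end with "lsmeans treatment / diff cl alpha = 0.1".
- Three of the four open with "proc mixed data = dataset method = reml". The log-scale ANCOVA block opens with "proc mixed data = dataset method = ml".

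Appendix 1 defines the primary analysis as an ANCOVA on log relative change with log baseline as covariate, so the log-scale ANCOVA block is the primary one. The SAP text names neither ML nor REML, and nothing in either document explains the difference in level or in estimation method.

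**The concern.** In an LSMEANS statement the CL option gives limits at level 100 × (1 − alpha)%. An alpha of 0.1 therefore gives 90% limits, and 80% limits need 0.2. If the printed options reach the production programs, the primary, secondary and tertiary tables and figures will carry 90% limits under an 80% label.

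The primary block has a second fault. ML divides the residual sum of squares by the number of observations instead of the residual degrees of freedom. Its standard error is therefore too small, and its interval too narrow for whatever level is requested. Unlike the alpha option, this also affects the p-values that Section 6.1.1 asks for.

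The study plans no formal hypothesis tests (Protocol 9.1.2; SAP 5.1), so estimates and intervals carry the interpretation. Part 1 results inform whether Part 2 is run and at which doses (Protocol 9.5; SAP 7.2). The level behind the error bars should not be in doubt.

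**Working it through.** **Inputs.** Protocol 9.2.1 gives 15 completers per group, a log-scale SD of 0.221 and a 25% placebo-adjusted decrease, to be detected at 5% one-sided with power above 90%. Part 1 has 5 groups, so n = 75. The primary model has 5 treatment means and 1 covariate slope, so residual df = 75 − 6 = 69. I take 0.221 as the residual SD; the protocol does not say whether it is covariate-adjusted.

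**The plan's own power figure.**
- Log effect = −ln(0.75) = 0.2877.
- SE = 0.221 × √(2/15) = 0.0807.
- Power at 5% one-sided is 97.3% (normal) or 96.7% (noncentral t, 28 df), in line with the stated >90%.

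**The confidence level.**
- The text says 80%; the code gives 100 × (1 − 0.1) = 90%.
- t(0.90, 69) = 1.294 and t(0.95, 69) = 1.667; ratio 1.288. The 90% limits are 29% wider on the log scale.

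**ML against REML.**
- The ML residual variance is SSE/75 and the REML variance is SSE/69.
- SE ratio = √(69/75) = 0.959, so the ML SE is 0.0807 × 0.959 = 0.0774, 4.1% too small.

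**Limits around a 25% reduction.** Half-width h = t × SE; limits = 100 × (0.75 × exp(±h) − 1). Actual coverage with ML = 2F(0.959t) − 1, where F is the t distribution function on 69 df.

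| Options | h (log scale) | Limits | Actual coverage |
|---|---|---|---|
| alpha 0.2, REML (the 80% text) | 0.1044 | −32.4% to −16.7% | 80% |
| alpha 0.1, REML | 0.1345 | −34.4% to −14.2% | 90% |
| alpha 0.1, ML (primary block as printed) | 0.1290 | −34.1% to −14.7% | 88.6% |
| alpha 0.2, ML (only alpha corrected) | 0.1002 | −32.1% to −17.1% | 78.1% |

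The two discrepancies pull the width in opposite directions but do not cancel: 0.1290/0.1044 = 1.236, so the printed primary block is still 24% wider than the 80% interval.

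**P-values.** With the ML standard error, a nominal two-sided p of 0.05 has true size 2 × [1 − F(0.959 × t(0.975, 69))] = 0.060.

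**The case against.** The strongest reply is that this is example code and the governing text is uniform. The dataset name is a placeholder. The log-scale blocks write the log function inside the MODEL statement, where PROC MIXED expects variable names, so the primary block has to be rewritten before it runs. A programmer following Sections 5 and 6 has a clear 80% instruction. The supporting SAS output that 5.2.4 and 5.2.5 require would show alpha beside the limits. With no decision rule resting on a limit, a slip would be visible and could be recomputed. All of this stands, and it limits the harm. It does not remove the contradiction in the only model code the SAP offers. The displayed alpha would not reveal the ML fault, since ML understates the standard error itself.

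It is also fair to ask whether 80% was intended. The 5% one-sided level in Protocol 9.2.1 corresponds to a two-sided 90% interval, and Protocol 2.2.1 and 4.3.1 quote 90% intervals from completed work. That makes 90% plausible, so the sponsor should confirm the level.

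Two further limits hold. The SAP never prescribes REML, so ML is an inconsistency with the other three blocks and an understated variance, not a breach of the text. The ML effect also shrinks if Part 2 is run and pooled: assuming 150 evaluable participants and 6 to 10 fixed-effect parameters, coverage at alpha 0.2 would be 78.4% to 79.1%.

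Separately, both MMRM blocks contain a baseline-by-day term that SAP 5.2.5, SAP Appendix 1 and Protocol 9.4.2 do not. That is a further reason to reconcile Appendix 3 with the text.

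**Conclusion.** The concern holds. Text and figure titles specify 80%, all four code blocks produce 90%, and the primary block alone uses ML. At Part 1 planning values the primary block's options give an interval 24% wider on the log scale than the one specified, with coverage of about 88.6%, which is neither 80% nor 90%.

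These figures assume 75 evaluable participants, 5 arms, one covariate and a residual SD of 0.221. The consequence arises only if the printed options are used; nothing here shows that wrong intervals were produced. Point estimates and the sample-size statement are unaffected. Standard errors and p-values do not depend on alpha but do depend on the ML choice. The 95% intervals for adverse-event risk differences (SAP 6.6.1) are a separate analysis. This should be fixed before analysis: the consequence is limited, but the contradiction reaches the primary endpoint and is cheap to remove.

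**What to change.** Confirm the intended level, then make text and code agree:

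- **If 80% stands**, as the SAP text indicates, set alpha to 0.2 in all four LSMEANS statements in Appendix 3.1.1 and 3.1.2.
- **If 90% was intended**, keep alpha at 0.1 and change 80% to 90% in 5.2.4, 5.2.5, the affected parts of Section 6 and the titles of Appendices 5.3 and 5.4.
- **In either case**, change the log-scale ANCOVA block in Appendix 3.1.2 from ML to REML, so that the primary interval and p-values have their nominal properties and the block matches the other three.

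The first route costs four alpha values and one method option. The second costs one method option plus text edits in about a dozen SAP sections and two appendix titles. Neither touches the design, the data or the sample size.

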#### Appendix 4. List of Abbreviations

[figure not shown]
Abbreviation	Term
Abs	absolute
AE	adverse event
ALKP	Alkaline Phosphatase
ALT	Alanine Aminotransferase
ANCOVA	analysis of covariance
ANOVA	analysis of variance
ApoA1	Apolipoprotein A1
ApoB 100	Apolipoprotein B100
ApoB 48	Apolipoprotein B48
ApoB Total	Apolipoprotein B Total
ApoC3	Apolipoprotein C3
ApoE	Apolipoprotein E
AST	Aspartate Aminotransferase
ATC	Anatomic Therapeutic Chemical
AUC	area under the curve
AUDIT	alcohol use disorders identification test
BA	bioavailability
BE	bioequivalence
BLQ	below the limit of quantitation
BOCF	baseline observation carried forward
BP	blood pressure
CAP ®	Controlled Attenuation Parameter
CBL	Change from baseline
CDARS	Clinical Data Analysis and Reporting System (of US Food and Drug Administration)
CI	confidence interval
CK18-M30	Cytokeratin-18-M30
CK18-M65	Cytokeratin-18-M65
C max	maximum observed concentration
CMH	Cochran-Mantel-Haenszel
CRF	case report form
CSR	clinical study report
DMC	data monitoring committee
EAC	event adjudication committee
ECG	electrocardiogram
E-DMC	external data monitoring committee
FAS	full analysis set
FDA	Food and Drug Administration (United States)
FPG	Fasting Plasma Glucose
FPI	Fasting Plasma Insulin
GCP	Good Clinical Practice

Abbreviation	Term
GGT	Gamma Glutamyl Transferase
GLIMMIX	generalized linear mixed-effects model with repeated measures
GMC	geometric mean concentration
GMFR	geometric mean fold rise
GMR	geometric mean ratio
GMT	geometric mean titer
HbA1C	Glycated Hemoglobin A1C
HDL-C	High Density Lipoprotein Cholesterol
HOMA-IR	Homeostatic Model Assessment for Insulin Resistance
hsCRP	High Sensitive C-Reactive Protein
ICD	informed consent document
ICH	International Council for Harmonisation
IRC	internal review committee
IST	independent statistical team
ITT	intent-to-treat
LDL	Low Density Lipoprotein
LLOQ	lower limit of quantitation
LOCF	last observation carried forward
LOD	limit of detection
LS	least-squares
LSM	least-squares mean
MAR	missing at random
MedDRA	Medical Dictionary for Regulatory Activities
mITT	modified intent-to-treat
MMRM	mixed-effects model with repeated measures
MMTT	mixed meal tolerance test
MNAR	missing not at random
N/A	not applicable
NNB	number needed to benefit
NNH	number needed to harm
NNT	number needed to treat
NOAEL	no-observed-adverse-effect level
Non-HDL-C	Non High-Density Lipoprotein Cholesterol
PBL	Percent change from baseline
PCSK9	Proprotein convertase subtilisin/kexin type 9
PD	pharmacodynamic(s)
PK	pharmacokinetic(s)
PP	per-protocol
PPAS	per-protocol analysis set
PRO	patient-reported outcome
ProC3	N-terminal pro-peptide of type III procollagen
ProC6	C-terminal fragment of the $\alpha 3$ chain of procollagen type VI
PT	preferred term

Abbreviation	Term
QTc	corrected QT
QTcF	corrected QT (Fridericia method)
qual	qualitative
RCBL	Relative change from baseline
RCDC	reverse cumulative distribution curve
RR	relative risk
SAE	serious adverse event
SAP	statistical analysis plan
SD	standard deviation
SGS	Statistical Guidance Standards
SOP	standard operating procedure
SUSAR	suspected unexpected serious adverse reaction
TA	therapeutic area
TBIL	Total bilirubin
TEAE	Treatment emergent adverse event
ULN	upper limit of normal
VCTE™	Vibration-Controlled Transient Elastography
VLDL	Very Low Density Lipoprotein cholesterol
WHO	World Health Organization
WHODD	World Health Organization Drug Dictionary
%CDT	% Carbohydrate-Deficient Transferrin

## Appendix 5. Graphical Representations

[figure not shown]
### Appendix 5.1. Box and Whisker Plot Representation for Changes/Percent Changes from Baseline at Week 6 by Treatment

[figure not shown]

**Note:** To be adapted for C3711005 design with correct total daily dose and orderd by ratio then by dosing regimen (eg BID vs QD). Only box, whiskers, median, arithmetic mean and outliers should be reported in this graphic (individual participant data [open circles within 5th and 95th whisker should not be included] only the individual values which are outliers/outside whiskers).

[figure not shown]
**Appendix 5.2. Box and Whisker Plot for Changes/ Percent Changes From Baseline by Treatment and Week**

**Note:** To be adapted for C3711005 design (eg weeks as legend) with correct total daily dose. Only box, whiskers, median, arithmetic mean and outliers should be reported in this graphic (individual participant data [open circles within 5th and 95th whisker should not be included] only the individual values which are outliers/outside whiskers).

**Appendix 5.3. LS Means and Placebo Adjusted LS Means with 80% CI from MMRM Analysis Over Time Versus Week per Treatment (to be adapted for C3711005 Design)**

**Appendix 5.4. Example for LS Means and Placebo Adjusted LS Means with 80% CI from ANCOVA Analysis at Week 6 per Treatment (to be adapted for C3711005 Design)**

**Appendix 5.5. Example for Figure Reporting Multiple Laboratory Parameters Over Time Simultaneously (to be adapted for C3711005 Design)**
